7.3.1. Rationale for Dose Selection

To date, STAP-001 has been studied in approximately 140 subjects, including healthy volunteers, subjects with panic disorder, individuals with a history of sedative abuse, subjects with photosensitive epilepsy, and in subjects with epilepsy with predictable seizure patterns. In all cases, the drug was generally well tolerated with dosing up to 2 mg. Sedation is a common side effect of alprazolam and also provides a pharmacodynamic marker of CNS activity. In all studies to date, the sedation observed has been temporally associated with peak plasma levels, which typically occur within a few minutes of dosing, and sedation tended to be more pronounced with the 2 mg dose. In Study 002-202 (see summary in Section 4.4.2), the effects on IPS were observed for the 0.5 mg, 1 mg and 2 mg doses. The IPS effect seemed similar for the 1 mg and 2 mg doses but there did appear to be a slightly greater extent and a longer duration of sedation at the 2 mg dose. Therefore, the 0.5 mg and 1 mg doses were initially chosen for this study.

The analysis of the first five patients in the open label feasibility part of this study (ENGAGE-E-001) has shown a 60% responder rate with the 1 mg dose. In addition, the plasma alprazolam

concentrations of the first subjects that were dosed have been low. A further analysis of the PK data from previous studies has shown that the 2 mg dose consistently provides a higher exposure to alprazolam during the first 2 minutes after administration, whereas the 0.5 mg or 1 mg doses provide more flat concentrations of alprazolam. Based on these analyses it is likely that 0.5 mg of Staccato alprazolam will not be an efficacious dose. Staccato alprazolam has been generally well tolerated with dosing up to 2 mg. Therefore, the two doses of Staccato alprazolam for the double-blind part of the study will be amended from 0.5 mg and 1 mg to 1 mg and 2 mg.

This document cannot be used to support any marketing authorization application and any extensions or variations thereof.

REDACTED COPY

8. SELECTION AND WITHDRAWAL OF SUBJECTS

Subjects eligible for enrollment in the study must meet all of the following inclusion criteria and none of the exclusion criteria.

8.1. Subject Inclusion Criteria

1. Subject is able to provide written, personally signed, and dated informed consent to participate in the study or will have a legally authorized representative (LAR) sign the informed consent on his or her behalf before completing any study related procedures.
2. Male or female ≥ 18 years of age.
3. Has an established diagnosis of focal or generalized epilepsy or focal and generalized epilepsy with a documented history of predictable seizure episodes that includes at least one of the following:
 - a. Generalized seizure episodes starting with a flurry of absence seizures or myoclonic seizures with a minimum duration of 5 minutes
 - b. Episodes of a prolonged focal seizure with a minimum duration of 3 minutes
 - c. Episodes of multiple (≥ 2) seizures within a 2-hour time period
4. Prior to randomization, has experienced ≥ 4 seizure episodes with predictable pattern during the last 4 weeks (qualification period) and no more than one week without a predictable seizure episode before entry into the in-patient unit.
5. Female participants (if of child-bearing potential and sexually active) and male participants (if sexually active with a partner of child-bearing potential) who agree to use a medically acceptable and effective birth control method throughout the study and for 1 week following the end of the study. Medically acceptable methods of contraception that may be used by the participant and/or his/her partner include abstinence, birth control pills or patches, diaphragm with spermicide, intrauterine device (IUD), surgical sterilization, and progestin implant or injection. Prohibited methods include: the rhythm method, withdrawal, condoms alone, or diaphragm alone.
6. Subject is able to comply by the requirements of the protocol, particularly the requirements and specific Institution policies during the in-patient stay.

8.2. Subject Exclusion Criteria

1. History or diagnosis of non-epileptic seizures (e.g. metabolic or pseudo-seizures).
2. History of status epilepticus in the 6 months prior to Screening
3. Has a progressive neurological disorder such as brain tumor, demyelinating disease, or degenerative central nervous system (CNS) disease that is likely to progress in the next 3 months

- Do not follow guidelines specified in the protocol (i.e., is noncompliant with protocol procedures)

In addition, subjects may be withdrawn for any medically appropriate reason or significant protocol violation, in the opinion of the Investigator.

Subjects who withdraw or are withdrawn from the study will not be replaced.

8.3.1. Subject Withdrawal Procedures

A subject who prematurely discontinues study participation should have all assessments performed per the Exit Procedures if possible.

If a subject terminates early from the study, the Investigator will record the reason(s) for early termination on the relevant electronic case report form (eCRF). The specific reason for the withdrawal should be carefully documented on the eCRF.

Adverse events resulting in subject early termination will be followed to the satisfactory resolution and determination of outcome, as ascertained by the Investigator (and/or Sponsor, or its designee); See Section 12.1.2: Adverse Events. The data will be recorded on the appropriate eCRF.

8.4. Emergency Unblinding of Treatment Assignment

In the case of a medical requirement to break the blind to determine appropriate treatment for an adverse event, unblinding of a subject's treatment assignment can be achieved through the study-specific Interactive Web Response System (IWRS). If possible, the Investigator should discuss the circumstances with the Medical Monitor prior to accessing unblinding information. In the event of a blind break, the Medical Monitor will be notified through the electronic data capture system. The subject for whom the blind is broken should be subsequently withdrawn from the study. The details regarding the process of breaking the blind are outlined in the Pharmacy Manual.

9. STUDY SCHEDULE AND PROCEDURES

Subjects enrolled in this study will undergo only those procedures described in this protocol. No study-related procedures can be performed prior to receiving informed consent from the subject or the subject's LAR. See the Schedule of Events and Schedule of Events – Procedures in CRU/EMU (Appendix 1A and Appendix 1B) for a summary of the study procedures.

9.1. Part 1: Open Label Feasibility

9.1.1. Screening Visit

At the Screening Visit, it will be confirmed that the subject meets all inclusion and exclusion criteria and the procedures described in the Schedule of Events (Appendix 1A) will be performed, including: a full neurological and physical examination; vital signs assessment; medical history; blood draw for routine labs; 12 lead ECG; and urine drug and alcohol screen. A urine pregnancy test will be performed on females of childbearing potential.

After screening, the doses of the background AEDs should be kept stable if possible. If dose changes are deemed necessary, continued study participation of the subject should be discussed with the Medical Monitor.

9.1.2. Qualification Phase

Subjects meeting all the requirements during the Screening visit will be given a Seizure Diary and asked to record their seizure episodes over the next 4 weeks. In order for the subject to remain eligible and qualify for the study, they will have to have at least 4 predictable seizure episodes, within the 28-day Qualification Period. The Qualification Period may be extended beyond 28 days up to 56 total days to provide flexibility for scheduling of the Qualification Visit and Treatment Visit. The 28 days of the seizure diary activity immediately prior to the Qualification Visit will be assessed for qualification. There will be a visit at the end of the Qualification Period, during which the subject will turn in their seizure diary. At the end of the Qualification Period, the Medical Monitor will review the Seizure Diary to confirm acceptable seizure frequency and subject's advancement into the Treatment Phase. Subjects meeting the qualification criteria will enter the CRU/EMU within 7 days from the end of the Qualification Period.

9.1.3. Treatment Phase

The first subjects enrolled in the study will participate in an open-label feasibility evaluation and enrollment in this phase will end when there are data from eight individual subjects having seizure events in the CRU/EMU. Subjects meeting eligibility and qualification criteria will be admitted to the CRU/EMU, be assessed for continued eligibility according to the procedures in the Schedule of Events – Procedures in CRU/EMU (Appendix 1B), and be hooked up with EEG recording electrodes which will remain in place for the duration of the study. It is required that a Staff Caregiver be present to provide 1:1 coverage with the subject while in the CRU/EMU to watch for signs of a seizure episode. After the EEG electrode hook-up is complete, each subject

will be assigned a single 1 mg STAP-001 device that will be removed from the pouch and dispensed to the Staff Caregiver until drug administration. At the onset of the predictable seizure episode, the Staff Caregiver will activate the device and give to the subject if the subject is capable of self-administration or will assist in helping the subject to administer the drug. The Staff Caregiver will signal the onset of the seizure event on the video EEG, start the stopwatch and mark the occurrence of the seizure event on a seizure diary. At 2 minutes after study drug administration, the Staff Caregiver will record whether the seizure event has ceased or is still ongoing. The Staff Caregiver will observe the subject for the next 2 hours and record seizure activity on a seizure diary during this time period. After this the Staff Caregiver will continue observation throughout the 24 hours following drug administration. If over the course of 7 days there is no treatable seizure episode, the subject will be dismissed, after completing Exit Procedures. Note that the procedures in the Schedule of Events for the treatment day are only conducted on the day there is a treatable seizure event and drug has been administered.

The feasibility data (with special emphasis on the drug administration and clinical assessment procedures) from these eight subjects will be analyzed and reviewed by the Sponsor and study team before continuing to enroll subjects in the double-blind part of the study. If necessary, the study protocol will be amended (for example, to change the drug administration procedure or to redefine the time frame for primary endpoint assessment) before starting the double-blind part of the study.

When multiple procedures are scheduled at the same time point, the VAS assessment should be performed first, immediately followed by the PK draw.

All *Staccato* doses will be administered as one puff from a single inhalation device by the subject with or without the assistance of the study Staff Caregiver. The exact time of administration and correct intake of the medication will be noted and recorded in the CRF.

Subjects should have minimal postural changes for the first 1.5 hours after administration of study drug.

9.2. Part 2: Double-Blind

9.2.1. Screening Visit

At the Screening Visit, it will be confirmed that the subject meets all inclusion and exclusion criteria and the procedures described in the Schedule of Events (Appendix 1A) will be performed, including: a full neurological and physical examination; vital signs assessment; medical history; blood draw for routine labs; 12 lead ECG; and urine drug and alcohol screen. A urine pregnancy test will be performed on females of childbearing potential. Device training including study drug administration procedures will be conducted. Training may include subject use of a practice 'dummy' device that does not contain any active drug.

After screening, the doses of the background AEDs should be kept stable if possible. If the dose changes are deemed necessary, continued study participation of the subject should be discussed with the Medical Monitor.

9.2.2. Qualification Phase

Subjects meeting all the requirements during the Screening visit will be given a Seizure Diary and asked to record their seizure episodes over the next 4 weeks. In order for the subject to remain eligible and qualify for the study, they will have to have at least 4 predictable seizure episodes, within the 28-day Qualification Period. The Qualification Period may be extended beyond 28 days up to 56 total days to provide flexibility for scheduling of the Qualification Visit and Treatment Visit. The 28 days of seizure diary activity immediately prior to the Qualification Visit will be assessed for qualification. There will be a visit at the end of the Qualification Period, during which the subject will turn in their seizure diary. At the end of the Qualification Period the Medical Monitor will review the Seizure Diary to confirm acceptable seizure frequency and subject's advancement into the Treatment Phase. Subjects meeting the qualification criteria will enter to the CRU/EMU within 7 days from end of the Qualification Period.

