11.1. Demographic Characteristics and Medical History

Demographic characteristics (i.e., gender, race and ethnic origin, date of birth, and calculated body mass index) will be collected at the Screening Visit, and detailed on the eCRF.

Thorough medical history, including EEG and brain imaging (MRI/CT) findings within the last 5 years, history of seizures, seizure pattern, frequency and characteristics during the last 12 months. Current medications, and co-morbidities will be collected at the Screening Visit and reviewed and updated at entry into the CRU/EMU for the Treatment Phase. Epilepsy history and seizure documentation are collated and submitted to the Epilepsy Study Consortium Review Board for review.

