13. STATISTICAL METHODS

13.1. Sample Size Rationale

There are no studies in the literature to provide reliable estimates of active treatment or placebo response rates for this study. Assuming a 10% drop-out/protocol violation rate, approximately 115 subjects will be enrolled in the double-blind part of the study to provide approximately 35 evaluable subjects per treatment arm. Enrollment may be stopped after 105 evaluable subjects have completed the study.

Approximately 30% of the overall study population randomized in the study may be subjects being treated with chronic daily benzodiazepines as part of their epilepsy management. Since the effect of concomitant chronic daily benzodiazepines use on study treatment is unknown, a 50% response rate for chronic benzodiazepines users on active treatment arms is assumed. For subjects who are not chronic benzodiazepines users, a response rate of 60% for active treatment arms is assumed. With up to 30% of study population being chronic benzodiazepines users and these response assumptions, a 57% response for the active treatment arm is targeted.

Power calculations assume a 2-sided test and significance level of 0.05 with 90% power and are based on the assumption that the proportion of responders with STAP-001 is 57% (best active treatment arm) whereas the assumed placebo responder rate is 20%.

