#### Primary Efficacy Endpoint

The primary efficacy endpoint will be the proportion of responders in each treatment group achieving seizure activity cessation within 2 minutes after the administration of the study drug and no recurrence of seizure activity within 2 hours. The primary endpoint will be analyzed with a chi-squared test. The overall treatment comparison, as well as pair-wise comparisons between each dose level and placebo will be performed. The estimates of the treatment difference versus placebo and their 95% confidence interval will be presented.

There will be no adjustment for multiple treatment group comparisons in this dose-ranging Phase 2b study. The dose-response relationship will be explored with a regression analysis.

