#### Secondary and Exploratory Efficacy Endpoints

Secondary and exploratory endpoints will be summarized by treatment group and if applicable, by assessment time point. Exploratory statistical testing may be performed if warranted. The Cochran-

Mantel-Haenszel (CMH) test for row-mean score difference will be used to test the treatment difference in the seizure episode severity. The Kruskal-Wallis test will be used to compare seizure frequencies. The time-to-next-seizure data will be summarized and displayed with Kaplan-Meier plots. No multiplicity adjustment will be implemented for exploratory tests.

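### The 28-day pre-dose seizure diary serves only as an entry check; using it as a covariate could sharpen the exploratory seizure counts, and slightly the responder difference, at negligible cost

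*Protocol*

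**What the plan says.** **Collection.** In Part 2, subjects keep a diary through the Qualification Period and turn it in at the Qualification Visit. Randomisation follows later, after admission to the unit (Protocol 7.2, 9.2.3). Protocol 9.2.2 states: "The 28 days of seizure diary activity immediately prior to the Qualification Visit will be assessed for qualification". The Medical Monitor then checks the frequency and clears the subject for the Treatment Phase. Inclusion criterion 4 sets a floor of four predictable episodes in four weeks, with no gap longer than a week, and sets no ceiling. Protocol 11.1 also collects "history of seizures, seizure pattern, frequency and characteristics during the last 12 months".

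**Randomisation.** The strata are inducing versus non-inducing AEDs and chronic daily benzodiazepine use (Protocol 7.2). Seizure frequency is not a stratum.

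**Analysis (SAP 3.3.1, matching Protocol 13.4.2).**
- Responders: "The primary endpoint will be analyzed with a chi-squared test".
- Counts over 0–4, 0–6 and 0–12 hours: "The Kruskal-Wallis test will be used to compare seizure frequencies".
- Time to next seizure: Kaplan-Meier summary and plot, with no between-arm test or hazard ratio named.
- Dose-response: a regression whose model and covariates are not stated.

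The counts and the time to next seizure are exploratory endpoints (SAP 2.2.1).

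**Baseline.** SAP 3.2 summarises baseline characteristics by arm, Table 14.1.3 covers seizure history, and SAP 3.6 has a general rule that treats pre-dose measurements as baseline. None of these names the 28-day diary count.

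**The concern.** The number of seizures in the 12 hours after dosing, and whether one occurs within 2 hours, may well depend on how often that subject usually seizes. The plan itself treats diary frequency as informative, because it uses it to choose subjects likely to have an episode during a short inpatient stay. With a floor and no ceiling, frequencies can differ widely between subjects.

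If the diary does predict the outcome, an unadjusted analysis leaves that variation in the error term. The dose-versus-placebo comparison is then wider than it needs to be, in a dose-ranging trial with about 35 subjects per arm. The counts are part of what the trial will say about effect beyond 2 hours. A covariate is credible only if it is named before unblinding, so the opportunity is lost if the SAP stays silent.

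**Working it through.** **1. The plan's own figure.** Inputs from Protocol 13.1: "Power calculations assume a 2-sided test and significance level of 0.05 with 90% power", responder rates of 57% and 20%, and enrolment "to provide approximately 35 evaluable subjects per treatment arm".

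n = [1.96·√(2·p̄·(1−p̄)) + 1.2816·√(p₁(1−p₁) + p₀(1−p₀))]² / (p₁−p₀)²

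With p̄ = 0.385: [1.96·√0.47355 + 1.2816·√0.4051]² / 0.37² = (1.349 + 0.816)² / 0.1369 ≈ 34.2, so 35 per arm. Power at 35 is 90.7%, and exact enumeration of the chi-squared test also gives 90.7%. The plan's figure reproduces.

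**2. Responder difference, unadjusted.** SE = √(0.4051/35) = 0.108. The 95% CI half-width is 1.96 × 0.1076 = 21.1 points.

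**3. Responder difference, adjusted.** The documents give no prognostic strength, so a range is assumed. Simulation (35 per arm, 1,500 trials per scenario) compared a logistic-standardised risk difference with the unadjusted one. Half-width = 21.1·√(variance ratio).

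| Assumed odds ratio per SD of covariate | Variance ratio, adjusted/unadjusted | Half-width (points) |
|---|---|---|
| 1 (uninformative) | 1.02 | 21.3 |
| 1.5 | 0.99 | 21.0 |
| 2 | 0.94 | 20.5 |
| 3 | 0.88 | 19.8 |

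A ratio of 0.88 corresponds to R² = 0.12. With effective n = 35/(1−R²), power is 93.4% at R² = 0.10 and 94.6% at R² = 0.15, against 90.7% unadjusted.

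**4. Seizure counts.** The documents give no event rate, dispersion or correlation, so every input here is an assumption. Simulated trials had one dose against placebo, 35 per arm and a rate ratio of 0.4. The diary distribution was assumed to have a median of 12 episodes per 28 days, log-SD 0.9 and a floor of 4. Power is Kruskal-Wallis versus Quade rank ANCOVA.

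| Scenario | Kruskal-Wallis | Quade | Gain (points) |
|---|---|---|---|
| Diary uninformative | 83% | 83% | 0 |
| Placebo mean 0.35 per 12 h | 33% | 35% | 2 |
| Mean 1 per 12 h, rank correlation 0.53 | 61% | 72% | 11 |
| *With extra between-subject variation (log-SD 0.5):* | | | |
| correlation 0 | 75% | 75% | 0 |
| correlation 0.24 | 71% | 73% | 2 |
| correlation 0.39 | 70% | 75% | 5 |
| correlation 0.52 | 62% | 72% | 10 |
| correlation 0.62 | 54% | 68% | 14 |

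The power levels shift with the assumed variation, so the gap within a row is the quantity to read. Under no treatment effect, both tests rejected in about 4–7% of trials.

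**5. Which rows are plausible.** The assumed diary distribution has a mean near 20 episodes per 28 days. There are 56 twelve-hour periods in 28 days, so this is 20/56 ≈ 0.36 per 12 hours. If each episode counts as one seizure, the 0.35 row applies and the gain is about 2 points. A mean of 1 requires several seizures per episode, and the episode count is then a looser proxy for the seizure count.

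**The case against.** The case for leaving the plan alone is substantial, and most of it stands.

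- **Nothing is invalid.** Randomisation makes the unadjusted chi-squared and Kruskal-Wallis tests valid. Chance imbalance in baseline frequency is sampling error already covered by the significance level.
- **The covariate and the outcome differ.** The diary criterion counts predictable episodes, while the endpoint counts seizures. Inclusion criterion 3 mixes absence or myoclonic flurries, prolonged focal seizures and clusters. A subject with a few large clusters and one with many isolated seizures could rank opposite ways on diary and outcome. High correlations are therefore the least credible.
- **The counts are exploratory.** SAP 3.3.1 leaves exploratory testing optional, so the choice of test there is partly preference.
- **The data may not be in the database.** The diary goes to the Medical Monitor. No section says that the 28-day count is entered in the eCRF, and no SAP listing names it.
- **Some use may already be intended.** Table 14.1.3 or the baseline summary could include the diary count, and the dose-response regression leaves its covariates open.

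These points limit the size and status of the issue but do not remove it. No efficacy analysis names the covariate, and adjustment costs almost nothing if the diary turns out uninformative.

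**Conclusion.** The point holds as a missed efficiency. The diary is collected before randomisation, its only stated use is eligibility, and no planned efficacy analysis adjusts for it. The count comparison, and to a lesser extent the responder difference, may be less precise than the data allow.

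The size is conditional on a prognostic strength that the documents do not give. For the counts, the assumed scenarios give about 0 to 10 points of power at rank correlations up to about 0.5. For responders, the variance ratio runs from about 1.02 to 0.88, which moves the CI half-width from 21.1 points to between 21.3 and 19.8.

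A reader might infer more than the documents support:
- *That the analyses are biased or the trial is underpowered.* They are not: the tests are valid, and the primary comparison has 90.7% power under the plan's assumptions.
- *That precision is certainly lost.* This is true only if diary frequency predicts outcome. At an odds ratio of 1 per SD, adjustment loses slightly.
- *That the gain is around 20 points.* Power can rise from 64% to 85%, but only with a mean of 1 seizure per 12 hours and a rank correlation of 0.67, which is a favourable corner.
- *That the time-to-next-seizure comparison loses precision.* No between-arm test is planned there, so there is no formal comparison to weaken.

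**What to change.** Before unblinding:

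1. In SAP 3.3.1 and Tables 14.2.5.3 and 14.2.5.4, prespecify a rank ANCOVA (Quade) of N_4h, N_6h and N_12h with the rank of the 28-day diary frequency as covariate. The Kruskal-Wallis result can stay beside it if the SAP says which one leads. Protocol 13.4.2 names Kruskal-Wallis, so record the change in SAP 3.7, which now reads as not applicable.
2. Keep the chi-squared test as the primary analysis. Add a supportive covariate-standardised responder difference with 95% CI, from a logistic model with log diary frequency. The entry floor of four episodes keeps the log defined for qualifying subjects.
3. Confirm that the 28-day count is entered in the database, define it among the derived variables in SAP 3.6, and summarise it by arm in Table 14.1.3.
4. Optionally, add a Cox model with log diary frequency for time to next seizure. This would be a new exploratory analysis, not a correction.

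The cost is SAP wording, a few lines of code and one degree of freedom. If the count was not entered, it must also be transcribed from diaries already collected. No new subject data are needed.
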